3.2.2 Male Participants

Men who meet any of the following criteria (by self-report, unless otherwise specified) will be excluded from this study:

• History of sensitivity/allergy to latex or any component of the study products.

- In the six months prior to Enrollment, diagnosed with or treated for any STD.
- Self-reported STD symptoms within the two weeks prior to providing informed consent for the study that cannot be attributed to a non-STD cause upon genital exam.

Note: Men who report current STD symptoms will be offered a genital exam and, if indicated, referred for appropriate clinical follow-up and/or treatment.

• Have any other condition that, in the opinion of the investigator, would preclude provision of informed consent, make participation in the study unsafe, complicate interpretation of study outcome data, or otherwise interfere with achieving the study objectives.

3.3 Recruitment Setting

Female study participants will be recruited primarily from infectious disease clinics associated with the four participating study sites, as follows:

- the Harlem Hospital Center and Bronx-Lebanon Hospital Center located in New York, NY;
- the Miriam Hospital and Women and Infants Hospital, located in Providence, RI.
- the 1917 Outpatient/Research Clinic at the Hospital of the University of Alabama at Birmingham, located in Birmingham, AL; and
- the Hospital of the University of Pennsylvania, located in Philadelphia, PA.

These hospitals all are located in urban areas and serve hundreds of HIV-infected women in each of the four study communities. Potentially-eligible participants also may be sought through a number of other mechanisms. For example, recruitment information may be distributed to medical staff and case managers at local HIV clinical practices to forward to potentially-eligible women. Women who have responded to previous research recruitment efforts or who have participated in previous research studies may be sought through newspaper ads, posting of flyers on public kiosks, and outreach at venues frequented by potentially-eligible women. Finally, this study will be listed with the US Department of Health and Human Services' AIDS Clinical Trials Information Service, which is accessible via phone (at [name]) and on the Internet (at www.actis.org).

3.4 Recruitment, Screening, and Enrollment Process

Recruitment, screening, and enrollment for this study will proceed in a step-wise manner over the course of at least two study visits (i.e., the Screening and two) for female participants and at least one study visit for male sexual partners. For participants who do not meet the study eligibility criteria, the process will be discontinued when ineligibility is determined.

Potential female study participants will be recruited as described in Section 3.3, and scheduled for a study Screening Visit to take place on any non-menstrual day. After providing written informed consent for both study screening and on-study procedures, recruited women will undergo the screening medical history, exam, and laboratory procedures described in Section 5.1. For sexually active participants, the screening process also will include ascertainment of whether the participant currently has a monogamous HIV-infected male sexual partner whom she is willing to involve in the study.

Women found to be presumptively eligible at the Screening Visit will be scheduled for an Enrollment Visit to take place 3-5 days following their next menstrual period, but within 42 days of the Screening Visit. (Women who are not enrolled within 42 days of screening must repeat all screening evaluations.) At this visit, female participants' eligibility will be confirmed according to the procedures described in Section 5.2; confirmed eligible participants will be randomized (see Section 7.4) and enrolled in the study.

As an additional factor for eligibility determination, sexually active participants' monogamous HIV-infected male sexual partners also must provide written informed consent for the study and have their eligibility confirmed prior to randomization and enrollment of the female participant. This may occur at any time between the female participant's Screening and Enrollment Visits, or concurrent with the female participant's Enrollment Visit.

3.5 Co-Enrollment Guidelines

Female participants in this study may be co-enrolled in other clinical trials (e.g., of HIV treatment regimens) at the time of screening and/or enrollment into this study, provided they meet the eligibility criteria for this study listed in Section 3.1 and 3.2. Specifically, participants must have stable HIV treatment regimens and must not have participated in any other microbicide or contraceptive research study within the 30 days prior to enrollment in this study. Once enrolled in this study, however, participants will be counseled not to join any other new clinical trial while taking part in this study.

Male partners who take part in this study may be co-enrolled in any other clinical trials.

3.6 Participant Retention

Once a participant has enrolled in the study, the study site will make every reasonable effort to retain him/her for the entire 14-day study period. One hundred percent retention of enrolled participants is targeted. Study sites are responsible for developing and implementing local standard operating procedures (SOPs) to achieve complete follow-up. Components of such SOPs include:

- Thorough explanation of the study schedule and procedural requirements during the informed consent process, and re-emphasis at each study visit.
- Collection of detailed locator information at the study Screening Visit, and active review and updating of this information at each subsequent visit.
- Use of appropriate and timely visit reminder mechanisms (e.g., phone calls on the day prior to the visit).
- Immediate and multifaceted (e.g., by phone, mail, e-mail, in person) follow-up on missed visits.
- Mobilization of trained outreach workers to conduct in-person contact with participants at their homes and/or other community locations.

3.7 Participant Withdrawal

Regardless of the participant retention methods just described, participants may voluntarily withdraw from the study for any reason at any time. The site investigator also may withdraw participants from the study in order to protect their safety and/or if they are unwilling or unable to comply with required study procedures.

Participants also may be withdrawn if the study sponsor or government or regulatory authorities terminate the study prior to its planned end date.

Every reasonable effort will be made to complete a final evaluation (as described in Section 5.5) of female participants who terminate from the study prior to Day 14. Male sexual partners will be asked to complete the follow-up acceptability assessment (as described in Section 5.6) if they or their partner withdraw from the study. Study staff will record the reason(s) for all withdrawals from the study in participants' study records.

4.0 STUDY PRODUCT

4.1 **Product Formulation**

4.1.1 CS Gel

Six percent CS gel contains 60 mg of the active ingredient, sodium cellulose sulfate, per milliliter of gel. Each 3.5 mL application of 6% CS gel therefore contains 210 mg of the active ingredient. The vehicle gel contains 20% glycerin as a humectant, 1.5% sodium carboxymethyl-cellulose as a thickener, 0.18% methylparaben and 0.02% propylparaben as preservatives, and water. The ingredients are United States Pharmacopeia/National Formulary grade materials. Addition of the active ingredient to the vehicle at a 6% concentration produces a thick gel that should be stored at room temperature. The pH of 6% CS gel is 7. The gel is slightly hazy in appearance with a light brown tint and is odorless.

Clinical supplies of CS 6% gel have been manufactured and packaged under good manufacturing practice conditions for this study by:

Personal Products Company Women's Health Division of McNeil-PPC, Inc. [name]

FDA Registration #2214133

4.1.2 Control Gel

The control gel is K-Y Jelly, a licensed, commercially available waterbased lubricant that contains chlorhexidine gluconate and methylparaben as preservatives as well as glucono delta lactone, glycerine, hydroxyethylcellulose, purified water, and sodium hydroxide. It is a clear, odorless gel that is slightly less viscous than 6% CS gel. It should be stored at room temperature. The gel has been packaged under good manufacturing practice conditions for this study into disposable, single-use applicators, and over-wrapped in pouches by:

Ortho Pharmaceutical Division of OMJ, Inc. [name]

FDA Registration #2650078

4.2 **Product Application Regimen**

Female participants will apply 3.5 mL of the assigned study product either once or twice daily for a period of 14 days, beginning on study Day 0 (i.e., the day of the Enrollment Visit). Participants will be instructed to remain recumbent for at least 15 minutes after each application and, if possible, to avoid emptying their bladder or bowel within the first hour after application.

- Participants in Cohorts 1 and 3 will apply the assigned product once daily, at bedtime.
- Participants in Cohorts 2 and 4 will apply the assigned product twice daily, in the morning and at bedtime, with an approximate 12-hour interval between applications. On study Day 7, participants in Cohorts 2 and 4 will be instructed to delay their morning application until after completion of their follow-up pelvic exam, unless the follow-up pelvic exam is scheduled in the afternoon.
- On days when participants in Cohorts 3 and 4 have vaginal intercourse, they will substitute coital application(s) 5-15 minutes prior to intercourse if at all possible for the routine daily application(s). However, the total number of daily applications will not exceed the assigned frequency. During these coital applications, it is understood that participants will not necessarily remain recumbent after application.

4.3 **Product Supply and Accountability**

CONRAD will provide both 6% CS gel and the control gel. Both products will be supplied in identical, single-use 3.5 mL applicators packaged in individual white wrappers. The packager prior to shipping the clinical supplies will verify the delivery volume of the pre-filled applicators.

Supplies of both products will be made available to the study sites through the NIAID Clinical Research Products Management Center (CRPMC). Site pharmacists will obtain supplies from the CRPMC according to the instructions in the manual "Pharmacy Guidelines and Instructions to DAIDS Clinical Trials Group," in the section entitled "Investigational Agent Control."

Site pharmacists must maintain complete records of all CS and control gel supplies received from the CRPMC and subsequently dispensed to study participants. All unused supplies must be returned to the CRPMC after the study is completed or terminated.

The HPTN Coordinating and Operations Center (CORE) will supply a single brand and type of lubricated latex male condom (not containing N-9) to each site for distribution to study participants. Sites will obtain unscented panty liners for distribution to participants.

4.4 Adherence Assessment

Participants will record on their Daily Study Records the date and time of each product application. The records also will collect information on the timing of sexual activity (if any), use (or non-use) of study and non-study condoms, use of other intravaginal products, and the emergence/resolution of any symptoms experienced. The investigator or designee will interview each participant and review her Daily Study Records at her Day 7 and Day 14 Follow-up Visits, along with the number of used and unused product applicators returned at these visits, to assess adherence to the study product use and sexual activity requirements.

Daily administration of the assigned study product at the assigned frequency on 14 consecutive study days is targeted, however lapses of consecutive day use will be accommodated, as follows:

- Participants in Cohorts 1 and 3 who miss an application on one day out of 14 will be instructed to complete one application on one additional day (as soon as possible after Day 13) to achieve a total of 14 days of exposure prior to onset of the next menstrual period.
- Participants in Cohorts 1 and 3 who miss an application on two days out of 14 will be instructed to complete one application on two additional days (as soon as possible after Day 13) to achieve a total of 14 days of exposure prior to onset of the next menstrual period.
- Participants in Cohorts 2 and 4 who miss one or two applications on one day out of 14 will be instructed to complete two applications on one additional day (as soon as possible after Day 13) to achieve a total of 14 days of exposure prior to onset of the next menstrual period.

• Participants in Cohorts 2 and 4 who miss one or two applications on two days out of 14 will be instructed to complete two applications on two additional days (as soon as possible after Day 13) to achieve a total of 14 days of exposure prior to onset of the next menstrual period.

Participants who complete twice daily administration of the assigned product on each study day between the Enrollment Visit (inclusive) and the Day 14 Followup Visit, as well as participants who adhere to one of the scenarios described above, will be considered adherent to the product use regimen. Participants who experience an AE that requires temporary suspension of product use at the instruction of the investigator for more than two days, but who are able to complete a total of 14 days of product use at the assigned frequency following resolution of the AE, prior to onset of the next menstrual period, also will be considered adherent. As well, participants who experience an AE that requires permanent product discontinuation, but completed daily administration at the assigned frequency on the days preceding the AE will be considered adherent.

For the sexually active cohorts (required to have vaginal intercourse at their usual weekly rate that must be at least twice per week), adherence is further defined as having at least two episodes of vaginal intercourse during the 14-day exposure period.

Non-adherent participants will be asked their reasons for non-adherence and this information will be recorded on study case report forms. If the participant is not willing to become adherent, the participant will be withdrawn from the study as described in Section 3.7. Non-adherent participants will not be replaced.

Note: Participants in the sexually active cohorts who have fewer than two episodes of vaginal intercourse between study Days 0 and 6 will be encouraged to resume their usual frequency of intercourse between Days 7 and 13.

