3.1.3 Sexually Active Female Participants

In addition to the criteria in Section 3.1.1, women must meet all of the following criteria in order to be eligible for inclusion in study Cohorts 3 and 4:

- Have been in a mutually monogamous relationship for at least three months with a male partner who is eligible for the study according to the criteria in Sections 3.1.4 and 3.2.2.
- Have a usual frequency of vaginal intercourse of at least two episodes per week with the male partner who meets the criteria in Sections 3.1.4 and 3.2.2.
- Agree, for the duration of the study, to:
 - have vaginal intercourse only with the male partner who meets the criteria in Section 3.1.4;
 - have vaginal intercourse at the usual frequency of at least two episodes per week with the male partner who meets the criteria in Section 3.1.4; and
 - use study-provided male condoms for each act of vaginal intercourse.
- Agree to abstain from vaginal intercourse during the 72 hours prior to the study Enrollment Visit.

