7.2.2 Secondary Endpoints

Consistent with the secondary study objective as listed in Section 2.2, the following secondary outcomes will be assessed:

- Participant "adherence" to the product use regimen, as defined in Section 4.4;
- Participant willingness to use the assigned study product during sexual intercourse in the future, as reported via the follow-up acceptability questionnaires.
- Reported positive aspects of using the assigned study product.
- Reported negative aspects of using the assigned study product.

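### The full-use adherence clause in Section 4.4 says twice daily for all women, so read literally it fails perfect users in the once-daily Cohorts 1 and 3

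*Protocol*

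**What the plan says.** Section 4.4 of the protocol opens with a target for every cohort: "Daily administration of the assigned study product at the assigned frequency on 14 consecutive study days is targeted". It then gives make-up rules by assigned frequency. Women in Cohorts 1 and 3 who miss one or two days add the same number of days with one application each. Women in Cohorts 2 and 4 add days with two applications each.

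The definition of adherence follows and has four routes:

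- Full use: "Participants who complete twice daily administration of the assigned product on each study day" from Enrollment to the Day 14 visit. No cohort is named.
- Made-up days: "as well as participants who adhere to one of the scenarios described above, will be considered adherent".
- Temporary suspension for an adverse experience (AE), then 14 days of use in total at the assigned frequency.
- Permanent discontinuation for an AE, after use at the assigned frequency up to that point.

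The frequencies are set in Section 4.2: "Participants in Cohorts 1 and 3 will apply the assigned product once daily, at bedtime", whereas "Participants in Cohorts 2 and 4 will apply the assigned product twice daily".

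For the sexually active cohorts, Section 3.1.3 requires agreement to "have vaginal intercourse at the usual frequency of at least two episodes per week with the male partner". Section 2.4.1 repeats the weekly requirement, and so does the sentence in Section 4.4 that goes on to say "adherence is further defined as having at least two episodes of vaginal intercourse during the 14-day exposure period".

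Section 7.2.2 makes adherence "to the product use regimen, as defined in Section 4.4" a secondary endpoint. Section 7.6.2 assesses it within treatment group and compares the gels across cohorts, with covariates for frequency of use and sexual activity. Section 7.3, as amended in August 2003, refers to the same definition when it describes a subgroup of 10 adherent women in Cohorts 1 and 2. Neither letter of amendment, as shown, changes Section 4.4.

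**The concern.** An endpoint rule should class as adherent a woman who does exactly what she was assigned to do. For Cohorts 1 and 3 the full-use clause demands a regimen that these women were not given. A programmer who codes Section 4.4 as written would record perfect once-daily users as non-adherent and women with one or two made-up days as adherent. The within-group adherence rates for the once-daily groups would then mean little. The fault also lies along frequency of use, which is one of the two covariates in the planned comparison, and it would carry into any adherent subgroup drawn from Cohort 1.

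The intercourse criterion is a smaller matter. The requirement is stated per week and the adherence threshold per 14 days, at the same count of two. The protocol does not explain the difference, so a reader cannot tell whether it is a tolerance or an oversight.

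**Working it through.** **Inputs.** Cohort sizes after the August 2003 letter: 24, 24, 12 and 20, total 80. Assigned frequency: once daily in Cohorts 1 and 3, twice daily in Cohorts 2 and 4 (Section 4.2). Exposure: 14 days.

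**1. Women under each clause.**
- Once-daily cohorts: 24 + 12 = 36; 36/80 = 45%.
- Sexually active cohorts: 12 + 20 = 32; 32/80 = 40%.

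**2. Applications under perfect use in Cohorts 1 and 3.** Assigned: 14 × 1 = 14. Under the literal full-use clause: 14 × 2 = 28.

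**3. Literal reading of each route for a woman in Cohort 1 or 3** (product use only):

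| Pattern of use | Route met | Literal result |
|---|---|---|
| Once daily on all 14 days, no AE | none | non-adherent |
| One or two days missed and made up | made-up days | adherent |
| Stopped or suspended for an AE, otherwise as assigned | AE clauses | adherent |
| Twice daily on all days | full use | adherent, though not as assigned |
| Three or more days missed, no AE | none | non-adherent |

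The first and fourth rows conflict with the assignment; the others do not. In Cohorts 2 and 4 the same product-use clauses agree with the assignment.

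**4. Intercourse, Cohorts 3 and 4.** Stated requirement over the exposure period: 2 per week × 2 weeks = 4 episodes. Needed to count as adherent: 2. Ratio 2/4 = 50%. Women with 2 or 3 episodes fall between the two statements.

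**5. The power figures that refer to the adherent subgroup.** The rule is 0 or 1 event, so the probability is (1−p)^n + n·p·(1−p)^(n−1).
- n = 10, p = 0.10: 0.9^10 + 10 × 0.1 × 0.9^9 = 0.349 + 0.387 = 0.736. At p = 0.45 it is 0.023.
- n = 20, p = 0.05: 0.95^20 + 20 × 0.05 × 0.95^19 = 0.358 + 0.377 = 0.736. At p = 0.25 it is 0.024.

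Both reproduce the 74% in Section 7.3. They depend only on the number of women and the event rate, so correcting the definition does not change them.

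**The case against.** The strongest reply is that the intent is plain. The target, the cohort-specific make-up rules and both AE clauses point to the assigned frequency, and Section 4.2 fixes once-daily use. Misclassification follows only if one phrase is applied against everything around it. That stands, and it limits the severity. It does not remove the error, because Section 7.2.2 adopts Section 4.4 as the endpoint definition.

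A reader might infer that the once-daily cohorts are scored upside down. They are not. What is inverted is perfect use against one or two made-up days; women with longer unexplained lapses still fail. Nor does the protocol set a general cap on daily applications: the explicit limit is given for intercourse days in Cohorts 3 and 4, and for Cohort 1 it follows only from the assignment.

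A reader might also infer a bias between gels. Randomization is stratified by cohort, so the wording is not differential by itself. It could become so only if made-up days or AEs differed between gels.

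On intercourse, the lower figure may be a deliberate floor. Section 4.4 accommodates lapses in product use, and its note on women with fewer than two episodes in Days 0 to 6 only asks that they be encouraged. The endpoint is also worded as adherence to product use, and Section 4.4 distinguishes product use from sexual activity requirements. These points stand, so the claim that every cohort except Cohort 2 is misclassified is not supported. Cohort 4 would be touched only if the intercourse criterion is part of the endpoint and the lower threshold is unintended.

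**Conclusion.** The full-use clause is wrong as written for Cohorts 1 and 3. It covers 36 of 80 women (45%). That is the number to whom the faulty clause applies, not an estimate of how many would be misclassified, which depends on how many use the gel perfectly and on whether the text is applied literally.

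The intercourse threshold for Cohorts 3 and 4 (32 of 80) is half the stated weekly requirement over two weeks. This is an unexplained mismatch between statements, not an established error, and no view is taken here on which figure should apply.

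The consequences stop at the secondary adherence endpoint and any adherent subgroup. Sections 7.6 and 7.6.1 include all randomized or enrolled women, so the primary safety tabulations do not depend on adherence. The point is a minor-to-moderate correction.

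**What to change.** In the full-use sentence of Section 4.4, replace *twice daily administration* with *administration at the assigned frequency*. This matches the rest of the section, leaves Cohorts 2 and 4 unchanged and costs one phrase.

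For Cohorts 3 and 4, reconcile the weekly requirement in Sections 2.4.1, 3.1.3 and 4.4 with the 14-day threshold. State whether the lower threshold is an intended tolerance, and whether intercourse is part of the Section 7.2.2 endpoint or a separate measure. Alternatively, report the proportions meeting each threshold, which needs no choice between them. Section 4.4 already has the Daily Study Records collect the timing of sexual activity, so this adds a line or two to a table and no data collection. Sample size and power statements stay as they are.

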After completing five to nine consecutive days of product application, participants will complete a study Follow-up Visit (target Day 7) during which their Daily Study Records will be reviewed — to assess adherence to the product use regimen and ascertain whether any adverse experiences have occurred — and a pelvic exam with colposcopy will be performed. After completing 12 to 14 days of product application, participants will complete a study follow-up visit (target Day 14) during which their Daily Study Records again will be reviewed and a pelvic exam with colposcopy will be performed at both Days 7 and 14. Hematology, coagulation, and liver and renal function testing, urine pregnancy and pathogen testing also will be performed. At any of the study follow-up visits, or at any ad hoc visits initiated by participants between scheduled visits, abnormalities noted on pelvic exam will be evaluated and followed according to Appendix II; continued/discontinued product use also will be guided by Appendix II.

The acceptability of CS gel will be assessed via questionnaires administered to both female participants and male partners. At their study Enrollment Visits, female participants will complete a behavioral questionnaire regarding their past history of vaginal product use. At Day 14, female participants will complete a follow-up acceptability questionnaire regarding their specific perceptions of the gel they applied during the study. The male partners of sexually active participants will complete a follow-up questionnaire regarding their perceptions and experiences with the gel within four weeks after the female participant has completed product use.

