5.5 Day 14 Follow-up Visit for Female Participants

(target Day 14, allowable Day 12-16)

- Update locator information.
- Administer follow-up acceptability assessment and study burden assessment.
- Collect used and unused product applicators, review the participant's Daily Study Records, and obtain interval medical history to assess adherence with protocol requirements and determine whether any AEs occurred since the last visit.
- Collect urine and conduct pregnancy and LE test; if LE test is positive (greater than trace), perform culture and microscopy at the LL.

- Perform pelvic exam with colposcopy, as follows:
 - naked eye exam of external genitalia,
 - speculum exam of vagina and cervix,
 - colposcopic exam and imaging of vulva, vagina, and cervix,
 - vaginal pH,
 - dried smear for Gram stain,
 - wet mount for trichomonas, candida, and BV,
 - sno-strip and CVL for HIV viral load at the HPTN CL, and
 - bimanual exam for adnexal or fundal masses or tenderness.
- Follow up on any abnormalities observed according to Appendix II.
- Collect blood and perform CBC, liver and renal function testing, and coagulation testing at the LL; process plasma for HIV RNA PCR at the HPTN CL.
- Complete and submit required data collection forms.

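### Full-use adherence in Section 4.4 is counted up to the actual Day 14 visit, which may fall on Day 12 to 16, although the regimen is fixed at Days 0–13 (minor)

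*Protocol*

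**What the plan says.** Section 4.2 has women apply product "for a period of 14 days, beginning on study Day 0", which is Days 0–13. Section 4.4 starts from the same standard: use "at the assigned frequency on 14 consecutive study days is targeted". Its lapse scenarios count missed days out of 14 and place make-up use after Day 13.

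Section 4.4 then defines adherence for a woman without lapses as use "of the assigned product on each study day between the Enrollment Visit (inclusive) and the Day 14 Followup Visit". Women who follow a lapse scenario form the other main group: "as well as participants who adhere to one of the scenarios described above, will be considered adherent". Two further routes cover women whose use was suspended or stopped because of an adverse experience.

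Section 5.5 gives the timing of the visit that closes the window: "target Day 14, allowable Day 12-16". Section 2.4.2 describes the same visit by days of use: "After completing 12 to 14 days of product application, participants will complete a study follow-up visit (target Day 14").

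Section 7.2.2 lists as a secondary endpoint "Participant 'adherence' to the product use regimen, as defined in Section 4.4". Section 7.6.2 compares it between the two gels with cohorts combined.

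**The concern.** The full-use window ends at a visit with a five-day allowance, while the regimen has a fixed length. A woman's adherence status can therefore depend on her appointment date as well as on her use of the product.

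The other routes do not share this feature. The lapse scenarios and the temporary-suspension route both count to a total of 14 days. The extra condition for Cohorts 3 and 4, on episodes of intercourse, also refers to the 14-day exposure period. In those cohorts the two parts of adherence would be counted over different windows.

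Section 7.2.2 takes its definition directly from Section 4.4, so the wording carries into a named endpoint. It would also decide who belongs to the adherent subgroup that Section 7.3 uses for its robustness statement.

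**Working it through.** **Inputs.** Regimen: Days 0–13 (Sections 4.2 and 4.4). Full-use window: Day 0, inclusive, to the Day 14 visit (Section 4.4). Visit day v: 12 to 16 (Section 5.5).

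**Day count.** With the visit day not counted, the required days are 0 to v − 1, so the number required is v. Compare this with a woman who used product on exactly Days 0–13, and with one who used it daily until a visit on day v and then stopped.

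| Visit day v | Days required | User of exactly Days 0–13 | Daily user who stops at the visit |
|---|---|---|---|
| 12 | 12 | not applicable at the visit | passes with 12 days |
| 13 | 13 | not applicable at the visit | passes with 13 days |
| 14 | 14 | passes | passes with 14 days |
| 15 | 15 | fails (no use on Day 14) | passes with 15 days |
| 16 | 16 | fails (no use on Days 14 and 15) | passes with 16 days |

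Only v = 14 matches the regimen. If the visit day is counted, the requirement becomes 13 to 17 days, and the 14-day user already fails at a Day 14 visit.

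**Do the other routes cover the late-visit woman?** The lapse scenarios apply to a woman who missed use on one or two days out of 14, and she missed none. The suspension and discontinuation routes require an adverse experience. No route covers her.

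**Side by side with Section 2.4.2.** That section expects the visit after 12 to 14 days of use. For visits on Day 15 or 16, the literal full-use rule demands 15 or 16 days, which exceeds both that range and the regimen.

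**Exposure to the error.** After the Letter of Amendment of 1 August 2003, each arm has 12 + 12 + 6 + 10 = 40 women. The distribution of visit dates is not given, so the following are assumptions.

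- All visits on Day 14: no woman is affected.
- 70% on Day 14: 30% are judged on a count other than 14, or 0.30 × 40 = 12 per arm.
- Even spread over five days: 2/5 = 40% are judged on fewer than 14 days and 40% on more, or 16 per arm each way.

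These figures count women whose required number differs from 14. Fewer would be misclassified, because some late visits will follow make-up days and pass by the lapse route.

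**Power figures.** Section 7.3 gives 74% power for 10 adherent women and 74% for 20 pooled. With P(0 or 1 event) = (1 − p)^n + np(1 − p)^(n−1):

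- n = 10: 0.736 at p = 0.10 and 0.023 at p = 0.45.
- n = 20: 0.736 at p = 0.05 and 0.024 at p = 0.25.

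Both stated figures are reproduced. Neither depends on how the adherence window is worded.

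**The case against.** The strongest reply is that the Day 14 visit is simply the name of a visit, and that the surrounding text shows nominal Day 14 was meant. Day 0 up to nominal Day 14 gives exactly Days 0–13. No passage tells a woman without lapses to apply gel beyond Day 13, so scoring her non-adherent for following Section 4.2 would be perverse. This is probably the intended meaning. However, the protocol does not state it, and Section 5.5 uses the same name for a visit with a five-day window. The contradiction in the wording stands.

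On the early side the objection largely succeeds. A reader might infer that women seen on Day 12 or 13 are wrongly credited and should be scored non-adherent. The documents do not support that. Section 2.4.2 expressly accepts 12 days of application at this visit. Section 5.5 has used and unused applicators collected and lists no re-supply, whereas Section 5.4 lists one at Day 7. Crediting a woman who used every dose until her product was collected is defensible, and marking her down would again make her status depend on the appointment. Nor does equal exposure require equal status: a woman seen on Day 14 with two missed days and no make-up left out assigned doses, while a full user seen on Day 12 did not. What remains is that Sections 2.4.2 and 5.5 do not agree with the 14-day count in Sections 4.2 and 4.4.

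An analysis plan that is not shown might settle the derivation. It would still have to depart from the definition to which Section 7.2.2 points.

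**Conclusion.** The point holds, at minor severity. As written, the full-use rule requires between 12 and 16 days of use for a 14-day regimen, and it fails a complete Days 0–13 user who is seen on Day 15 or 16.

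Three stronger conclusions are not supported:

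- **A large share misclassified.** The 30% and 40% figures rest on assumed visit distributions, and the effect is nil if visits fall on Day 14.
- **A biased comparison of the gels.** Assignment is randomised within cohort and site (Section 7.4) and blinded (Section 7.5). The documents give no reason for visit timing to differ by gel. The likely result is noise and a distorted overall adherence rate.
- **Harm to the safety conclusions.** The primary tabulations include all enrolled women (Section 7.6.1), the accrual-suspension rule in Sections 2.4.3 and 6.1 does not use adherence, and the power figures do not change.

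The conclusion assumes that the full-use sentence is read at the assigned frequency for every cohort. Its reference to twice-daily use is a separate matter.

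**What to change.** In Section 4.4, define the full-use window as the 14-day exposure period (Days 0–13, with the make-up scenarios already listed), whatever the date of the Day 14 visit. Derive the endpoint from the dated applications in the Daily Study Records.

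For visits on Day 12 or 13, reconcile Section 2.4.2 (12 to 14 days of application) and Section 5.5 (applicators collected, no re-supply listed) with Sections 4.2 and 4.4. State how such women are classified for the adherence endpoint and report their days of use alongside. Do not score them non-adherent automatically.

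The cost is one reworded sentence and one added sentence. No new data are needed, since Section 4.4 already has the date and time of each application recorded. No sample size or power figure changes. The reported adherence rate may rise slightly for late visits.
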